6.3. Analysis Visit Window

Data analyzed by-visit-analysis (including all efficacy data, physical exam, vital signs, biomarker) will be summarized by the study scheduled visits described in the study protocol and SAP, "Schedule of Event". The analysis visit windows will be exhaustive so that all available values obtained from unscheduled visits, ET visits and EOT/EOS have the potential to be summarized.

The following analysis visit windows for all by-visit analysis will be used to map the unscheduled visits, ET and EOT/EOS visits, based on the study day:

visit	Targeted Study Days*	Analysis Window in Study Days
Screening	<1	<1
Baseline	1	1
Week 2	15	[2, 22]
Week 4	29	[23, 43]
Week 8	57	[44, 71]
Week 12	85	[72, 99]
Week 16	113	[100, 127]
Week 20	141	[128, 155]
Week 24(End of Treatment) (End of Study)	169	>=156

*study day is calculated relative to the date of first study drug injection.

In general, the following order will be used to select the record for analysis at a given visit:

3. Scheduled visit
4. Early termination (ET) or EOS, whichever comes first if scheduled visit is not available
5. Unscheduled visit if both scheduled visit and ET/EOT/EOS are not available

For the multiple measurements of the same test in the same window, the following rules will be used to pick up the analysis value:

- If multiple valid values of a variable are within an analysis visit window, the closest from the target study day will be selected.
- If the difference is a tie, the value after the targeted study day will be used.
- If multiple available values of a variable exist within a same day, then the first value of the day will be selected.

For the daily collected ePRO data, the analysis visit windows will be implemented following the procedure below:

Step 1: Derive the study day,

- If diary date \geq 1st injection date, then diary study day=diary date – 1st injection date +1;

- Otherwise diary study day=diary date – 1st injection date

Step 2: Windows are defined as -6 to 1 = BL, 2 to 8 = week 1, 9 to 15 = week 2, etc, with 7-day intervals between visit windows.

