8.3. Rescue Treatments

For participants who receive rescue treatment during treatment period, observed efficacy results will be analyzed in this study.

If medically necessary (ie, to control intolerable AD symptoms), rescue treatment for AD may be provided to study participants at the discretion of the investigator. Although the use of rescue medications is allowed at any time during the study, the use of rescue medications should be delayed, if possible, for at least 14 days following the initiation of the investigational treatment. If possible, investigators are encouraged to consider rescue initially with topical treatment (eg, medium/high potency TCS) and to escalate to systemic medications only for participants who do not respond adequately after at least 7 days of topical treatment. Topical calcineurin inhibitors may be used for rescue, alone or in combination with TCS, but the use of TCI should be reserved for problem areas only (eg, face, neck, intertriginous and genital areas, etc). Investigators may also consider rescue with crisaborole. Rescue treatment for these topical therapies should be used as per prescribing information and local guidelines. Participants may continue study treatment if rescue consists of topical medications.

Participants who receive systemic corticosteroids or systemic nonsteroidal immunosuppressive drugs (eg, cyclosporine, methotrexate, mycophenolate mofetil, azathioprine, etc) as rescue medication during the study will be discontinued permanently from the study drug. All participants will be asked to complete the scheduled study visits and assessments whether or not they complete study treatment and whether or not they receive rescue treatment for AD. Investigators should make every attempt to conduct efficacy and safety assessments (eg, disease severity scores, safety laboratory tests) before administering any rescue treatment. An unscheduled visit may be used for this purpose, if necessary. For the purpose of efficacy analysis, participants who receive rescue treatment during the study will be considered treatment failures.

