9.1.1. Footnotes for the Schedule of Events Table**9.1.1.1. Table 1 Schedule of Events**

1. In light of the public health emergency related to COVID-19, the continuity of clinical study conduct and oversight may require implementation of temporary or alternative mechanisms. Examples of such mechanisms may include, but are not limited to, any of the following: phone contact, virtual visits, telemedicine visits, online meetings, non-invasive remote monitoring devices, use of local clinic or laboratory locations, and home visits by skilled staff. Additionally, no waivers to deviate from protocol enrollment criteria due to COVID-19 will be granted. All temporary mechanisms utilized, and deviations from planned study procedures in response to COVID-19 are to be documented as being related to COVID-19 and will remain in effect only for the duration of the public health emergency.
2. The length of the screening period is not fixed but must not exceed 35 days.
3. All visit 10 assessments should be performed if a participant terminates the study after the baseline visit and prior to the visit 10 window (early termination visit).
4. Eligibility based on age and weight at time of screening visit.
5. Assent collected from participant, if applicable, based upon the age of the participant.
6. The questionnaires will be administered only to those participants who speak fluently the language(s) in which the questionnaire is presented (based on availability of validated translations). Patient-reported assessments are completed only by the participant.
7. Training of participants/parents/caregivers regarding completion of diary at visit 1 to record assessment of PP NRS and Sleep Quality NRS. Provide additional training as necessary based on review of diary use.
8. Dupilumab to be dosed as per USPI. Study drug administration will occur Q2W. Q2W study drug administrations must be separated by at least 11 days. At the baseline visit, study drug will be administered at the clinic and thereafter study medication will be provided to participants for administration at home. If the investigator and participants (\pm parent/guardians as appropriate) agree, participants may return to the clinic for dupilumab administration (as prescribed) instead.
9. Last scheduled dose of dupilumab during the treatment period will be at week 22.

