11. STATISTICAL PLAN

11.1. Statistical Hypothesis

There is no formal statistical hypothesis testing and no planned inferential comparisons in this study.

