11.2. Justification of Sample Size

The enrolled population will attempt to approximate the US census bureau data on proportions of self-reported races that comprise the skin of color population in the United States— to this end all self-reported races representing skin of color will be included, however a cap at approximately 40% will be set for non-black/non-African American participants.

Due to the descriptive character of this study, no formal sample size calculation will be performed. The sample size of this study is chosen empirically to support descriptive analysis of efficacy and safety in the overall skin of color population. With up to a potential 15% drop out rate based on prior studies, 120 participants would yield approximately 105 participants overall.

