5.7.1. Analysis of Primary Efficacy Endpoint (EASI-75)

Primary analyses:

All observed data, regardless of whether rescue treatment is used, or data is collected after study drug withdrawal, will be used to analyze the primary endpoint. Percent of patients achieving EASI-75 at week 24 will be reported. The numerator is the number of patients who achieving EASI-75 at week 24, and the denominator is the number of patients who completed assessment EASI at week 24. Patients with missing data will not be imputed as non-responders. The primary efficacy analyses will be performed on FAS.

Sensitivity analyses:

1. Last observation carried forward – non-responder imputation (LOCF-NRI) approach:

For patients with missing data at week 24 who completed at least 16 weeks of treatment, missing data will be imputed by LOCF from either week 16 or week 20. Patients who received rescue therapy after week 16 will be considered non-responders.

2. Multiple imputation (MI) approach:

Efficacy data through week 24 after rescue medication use will be set to missing first. Missing data will be imputed by MI for 20 times based on patients who have non-missing data. The imputed week 24 EASI will determine EASI-75 response status.

Missing data from the FAS will be imputed 20 times to generate 20 complete data sets by using the SAS procedure MI following the 2 steps below:

Step 1: The monotone missing pattern is induced by Markov Chain Monte Carlo (MCMC) method in SAS procedure MI. The monotone missing pattern means that if a patient has missing value for a variable at a visit, then the values at all subsequent visits for the same variable are all missing for the patient.

Step 2: The missing data at subsequent visits will be imputed using the regression method for the monotone pattern with adjustment for covariates disease severity, and relevant baseline covariates.

The imputation model will include:

- The covariates included the EASI baseline value, the disease severity [IGA 3 vs IGA 4] and measured endpoint values from every clinic visit up to week 24

Week 24 data for each of the 20 complete datasets will be analyzed for EASI-75 response. The SAS MIANALYZE procedure will be used to generate valid statistical inferences by combining results from the 20 analyses using Rubin's formula.

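### Sensitivity analysis 1 for EASI-75 carries forward the scheduled week 16 or week 20 EASI even when a later early-termination EASI was collected in the same window

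*SAP*

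**What the plan says.** Three provisions meet here.

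- **Collection.** EASI is on the ET visit schedule (Protocol Table 1), and footnote 3 says: "All visit 10 assessments should be performed if a participant terminates the study after the baseline visit".
- **Record selection.** SAP 6.3 places ET, EOT/EOS and unscheduled assessments into windows by study day. Week 16 is days 100-127, week 20 is days 128-155, and week 24 is day 156 onward. It continues: "In general, the following order will be used to select the record for analysis at a given visit". The scheduled visit comes first. Second is "Early termination (ET) or EOS, whichever comes first if scheduled visit is not available". Unscheduled visits come last. A further rule in the same section reads: "If multiple valid values of a variable are within an analysis visit window, the closest from the target study day will be selected". A tie goes to the value after the target day. The SAP does not say how this rule relates to the ranking.
- **Imputation.** SAP 5.7.1, sensitivity analysis 1, applies when week 24 is missing and at least 16 weeks of treatment were completed: "missing data will be imputed by LOCF from either week 16 or week 20". Participants rescued after week 16 count as non-responders.

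**The concern.** An analysis named last observation carried forward should use the last observation. Read together, the ranking in SAP 6.3 and the restriction in SAP 5.7.1 allow the EASI taken at withdrawal to be passed over in favour of one taken up to several weeks before.

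This matters because the primary analysis counts only participants assessed at week 24. Those who leave without that assessment enter the EASI-75 result only through the two sensitivity analyses. Protocol 11.4.3.2, under secondary efficacy, also describes carrying forward the last post-baseline observation after drop-out for lack of efficacy. For such a participant that observation would normally be the ET assessment.

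**Working it through.** **The plan's own figure.** No error rate or power is involved: "There is no formal statistical hypothesis testing and no planned inferential comparisons in this study". The only sample-size figure is: "With up to a potential 15% drop out rate based on prior studies, 120 participants would yield approximately 105 participants overall". 120 × (1 − 0.15) = 102, against about 105 stated; 105 corresponds to 15/120 = 12.5% loss. The gap does not affect this point. The figures serve only to give a denominator range of 102 to 120, because SAP 5.7.1 does not state the denominator for this analysis.

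**Can a scheduled visit and a later ET share a window?** The visit windows in Protocol Table 1 are ±7 days. Week 16: 113 ± 7 = days 106-120, inside 100-127. Week 20: 141 ± 7 = days 134-148, inside 128-155. So yes, in both windows.

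**Worked case.** Visit 9 falls on day 141 and ET on day 150. Both lie in 128-155. A scheduled visit is available, so the day 141 record becomes week 20. Week 24 is missing, so day 141 is carried forward although a day 150 EASI exists. If the SAP means nominal week 16 and week 20 visits and not windowed records, the day 150 value is still not used.

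**Which ET days are affected?** Take visits on days 113 and 141, and ET on any day from 114 to 155 except 141.

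| ET day | Days | Value carried to week 24 |
|---|---|---|
| 114-127 | 14 | Day 113; ET not used |
| 128-140 | 13 | ET, as the week 20 record |
| 142-155 | 14 | Day 141; ET not used |

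Affected: 14 + 14 = 28 of 41 days (28/41 = 68%). An ET on day 156 or later falls in the week 24 window and needs no LOCF.

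**Does the closest-to-target rule change this?** Suppose it overrode the ranking. Let the scheduled visit fall 7 days early to 7 days late, and the ET on any later day in the same window. The number of day pairs per window is 21 + 20 + … + 7 = 210. The ET is preferred only when the scheduled visit was k days early (k = 1 to 7) and the ET lies no more than k days after target. That is 2k pairs for each k, and 2 × (1 + … + 7) = 56 in total. So ET wins in 56/210 = 27% of pairs and the scheduled record in 154/210 = 73%. With an on-target visit the scheduled record always wins.

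**How old is the carried value?** It precedes the ET by 1 to 14 days with on-target visits. The maximum is 21 days, for example a scheduled visit on day 106 and ET on day 127.

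**Size per participant.** One changed EASI-75 status is worth 1/120 = 0.8 to 1/102 = 1.0 percentage points. All drop-outs together number at most 0.15 × 120 = 18 under the planning assumption, and only some could fall in these windows.

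**Week 24 window.** Footnote 3 places ET before the visit 10 window, which opens on day 169 − 7 = 162. An ET on days 156-161 is therefore already in the week 24 window. Protocol 9.1.2 asks withdrawn participants to come back for the week 24 visit. If one returns on day 169, the result depends on how visit 10, labelled EOT/EOS, is ranked. Ranked as scheduled, day 169 is used. Ranked as EOS, the ET is used because it came first.

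**The case against.** The strongest reply is that the LOCF source is openly pre-specified, that preferring scheduled over event-triggered records is defensible, and that the effect is confined to one descriptive sensitivity analysis alongside a separate multiple-imputation analysis. An ET with no scheduled visit in its window is used. All of that stands, and it limits the weight of the point. It does not explain why a last-observation analysis should skip an EASI that the protocol requires at withdrawal.

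Four stronger readings are tempting, and the documents do not support them.

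- **That the rule biases EASI-75 toward response.** The documents give no reasons for withdrawal. Rescue after week 16 already yields non-response, and participants who stop study drug are asked to keep attending visits (Protocol 8.4.2), so stopping treatment need not lead to an ET. Disease may have worsened, improved or stayed the same between the two assessments.
- **That pre-rescue unscheduled assessments are lost in the same way.** Protocol 8.3 asks for assessment before rescue and adds: "An unscheduled visit may be used for this purpose, if necessary". After week 16 the rescued participant is a non-responder whichever record is selected, so this has no effect here.
- **That the 68% yields an expected shift in the rate.** It counts days under exact attendance. Turning it into percentage points needs an assumed number of late drop-outs and an assumed share who change status, and neither is in the documents.
- **That the two selection rules contradict each other outright.** They can be read in sequence, with the ranking first and closeness then separating records of equal rank. The week 24 conflict also disappears if visit 10 counts as scheduled. The SAP states neither.

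**Conclusion.** The point holds within narrow limits. It applies to a participant who has completed 16 weeks of treatment, was not rescued after week 16, has no week 24 EASI, and attended an ET after the scheduled visit in the week 16 or week 20 window. For that participant the LOCF analysis carries an earlier EASI although a later one was collected. When the scheduled visit is on target, this is so under either reading of SAP 6.3.

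The number of such participants and the direction of any effect cannot be known from the documents. The conclusion rests on SAP 5.7.1 meaning either the windowed or the nominal week 16 and week 20 records; both lead to the same result in the worked case. The LOCF defect does not reach the primary analysis. The ranking of visit 10 could, because it decides which week 24 EASI is used, but that is a matter of clarity and not a demonstrated error.

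**What to change.** - **SAP 5.7.1, sensitivity analysis 1.** For the participants it already covers, carry forward the latest valid EASI by date at or after week 16, including the ET assessment, in place of the windowed week 16 or week 20 record. Say explicitly whether unscheduled assessments count; the point does not depend on the answer.
- **SAP 6.3.** State that visit 10 (EOT/EOS) ranks as a scheduled visit, so that a week 24 return visit is chosen over an earlier ET in the window from day 156. State also that the closest-to-target rule applies only among records of equal rank.

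The cost is a few sentences and a little programming. No new data are needed, since EASI is already collected at ET. The sensitivity rate might turn out less favourable.

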Administer dupilumab ^{8,9,10}		X		X	X	X	X	X	X		
Patient diary recording dosing information		X	X	X	X	X	X	X	X		
Concomitant Medications/procedures	X	X	X	X	X	X	X	X	X	X	X
Efficacy: ¹⁰											
Patient Reported:											
Peak Pruritus NRS ^{6,11}								X (daily)			
Sleep Quality NRS ^{6,11}								X (daily 7 days prior to each visit)			
Skin Pain NRS ⁶		X		X	X	X	X	X	X	X	X
Dyspigmentation NRS ⁶		X		X	X	X	X	X	X	X	X
Xerosis NRS ⁶		X		X	X	X	X	X	X	X	X
CDLQI ^{6,12} , DLQI ^{6,12}		X		X	X	X	X	X	X	X	X
HADS ⁶		X		X	X	X	X	X	X	X	X

Table 1: Schedule of Events¹		TREATMENT PERIOD									
Study Procedure	SCNV1²	BL V2	Ph V3	V4	V5	V6	V7	V8	V9	ET Visit³	EOT / EOS V10
Week (W)			W1	W2	W4	W8	W12	W16	W20		W24
Day (D)	D-35 to D-1	D1	D8	D15	D29	D57	D85	D113	D141		D169
Visit Window (Days [d])			±3 d	±3 d	±3 d	±7 d	±7 d	±7 d	±7 d		±7 d
POEM ⁶		X		X	X	X	X	X	X	X	X
Patient Global Impression of Disease ⁶		X		X	X	X	X	X	X	X	X
Patient Global Impression of Change ⁶				X	X	X	X	X	X	X	X
Investigator Reported:											
EASI	X	X		X	X	X	X	X	X	X	X
IGA	X	X		X	X	X	X	X	X	X	X
SCORAD		X		X	X	X	X	X	X	X	X
BSA	X	X		X	X	X	X	X	X	X	X
AD phenotypic description ¹³		X		X	X	X	X	X	X	X	X
Post-inflammatory hyperpigmentation severity scale (PHSS)		X		X	X	X	X	X	X	X	X
Photography (select sites) ¹⁴		X						X		X	X
Colorimetry measurement (select sites) ¹⁵		X		X	X	X	X	X	X	X	X
Optical Coherence Tomography and non-invasive in vivo imaging (single site) ¹⁶		X			X			X		X	X

Table 1: Schedule of Events¹		TREATMENT PERIOD									
Study Procedure	SCNV1²	BL V2	Ph V3	V4	V5	V6	V7	V8	V9	ET Visit³	EOT / EOS V10
Week (W)			W1	W2	W4	W8	W12	W16	W20		W24
Day (D)	D-35 to D-1	D1	D8	D15	D29	D57	D85	D113	D141		D169
Visit Window (Days [d])			±3 d	±3 d	±3 d	±7 d	±7 d	±7 d	±7 d		±7 d
Safety:¹⁰											
Physical Examination	X									X	X
Weight / Height	X									X	X
Adverse Events ¹⁷	X	X	X	X	X	X	X	X	X	X	X
Laboratory Testing:^{10, 19a}											
Pregnancy Test (Urine, WOCBP only)		X		X	X	X	X	X	X	X	X
Pharmacokinetics Sampling:¹⁸											
Drug conc. sample ¹⁹		X					X			X	X
Biomarkers:¹⁹											
Total serum IgE and allergen- specific IgEs		X			X		X			X	X
Exploratory Research Serum/Plasma		X			X		X			X	X
Future Biomarker Serum/Plasma (optional)		X			X		X			X	X
Pharmacogenomics:											
Whole blood for DNA (optional) ²⁰		X									

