10. Assessments/procedures should be conducted in the following order: Patient-Reported Outcomes (PROs), investigator assessments, safety and laboratory assessments, administration of study drug. Clinical sites will check participant data collected on the diary. Topical emollient (moisturizer) should be applied twice daily, as per physician's recommendation starting at the screening visit. Participants should continue to apply moisturizers throughout the study. However, to allow adequate assessment of skin dryness, moisturizers should not be applied on the day of the study visit.

11. These assessments are to be completed by study participants in their diaries: Peak Pruritus NRS will be conducted daily starting 7 days prior to baseline. Sleep Quality NRS is to be collected daily for 7 days immediately preceding the baseline visit and all subsequent visits.
12. CDLQI for participants <16 years of age, DLQI for participants ≥ 16 years of age.
13. AD phenotypic description (primary morphologies, and distribution) includes the following: Localized AD, Flexural AD, Extensor AD, Nummular AD, AD with prurigo nodules, Follicular AD, Papular AD, Lichenoid AD, and Psoriasiform AD
14. A photography substudy will be performed at a subset of study sites. Site training will be provided. Participant/parents or legal guardians who agree to participate in the substudy will be required to sign a separate substudy informed consent/assent form for use of photographs for educational/marketing purposes before the procedure is performed.
15. A colorimetry substudy will be performed at a subset of study sites. Site training will be provided. Participant/Parents or legal guardians who agree to participate in the substudy will be required to sign a separate substudy informed consent/assent form before the measurements are performed.
16. An OCT substudy with additional non-invasive in vivo imaging including line field confocal OCT and/or reflectance confocal microscopy at the discretion of the investigator will be performed at a single study site. Participant/Parents or legal guardians who agree to participate in the substudy will be required to sign a separate substudy informed consent/assent form before the procedure is performed.
17. Any participant who experiences an AESI related to an eye disorder will be referred to an ophthalmologist if deemed necessary by the investigator.

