9.2.2.1.1. Peak Pruritus NRS (PP NRS)

The PP NRS is a simple assessment tool that participants will use to report the intensity of their pruritus (itch) during a 24-hour recall period. Participants will be asked the following question:

For maximum itch intensity: “On a scale of 0 to 10, with 0 being ‘no itch’ and 10 being the ‘worst itch imaginable’, how would you rate your itch at the worst moment during the previous 24 hours?”

Participants will be instructed on using the participant diary to record their PP NRS at the screening visit. Participants will complete the rating scale daily throughout the entire study (baseline and preceding 7 days and treatment period; see [Table 1](#)). Clinical sites will check and remind the participant to complete the diary according to the time points in [Table 1](#).

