9.2.2.1.2. Sleep Quality NRS

Study participants will be asked to rate their sleep quality on their past night upon awakening, using the Sleep Quality NRS, ranging from 0 (“Worst possible sleep”) to 10 (“Best possible sleep”). Sleep Quality NRS are to be collected daily including 7 days immediately preceding the baseline visit and then daily during the week before each planned visit.

Participants will be instructed on using the participant diary to record their Sleep Quality NRS at the screening visit. Clinical sites will check and remind the participant to complete the diary according to the time points in [Table 1](#).

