The baseline NRS is defined as the prorated average of the NRSs reported continuously for 7 days right before and on the baseline visit (i.e. study day -6 to day 1). For post-baseline NRS, the mean weekly NRS is calculated as the prorated average of the reported daily NRS within the week. For example, if there are 3 scores in a week, the prorated average = (score1 + score2 + score3)/3.

Body Surface Area Affected by Atopic Dermatitis

The BSA affected by AD will be assessed for each major section of the body (the possible highest score for each region is: head and neck [9%], anterior trunk [18%], back [18%], upper limbs [18%], lower limbs [36%], and genitals [1%]) and will be reported as a percentage of all major body sections combined. Patients will undergo this assessment at baseline and subsequent study visits as indicated in Section 10.2.

Dermatology Life Quality Index (DLQI)

The DLQI is a 10-item, validated questionnaire ([Badia 1999](#)) used in clinical practice and clinical trials to assess the impact of AD disease symptoms and treatment on Quality of Life (QoL). The format is a simple response to 10 items, which assess QoL over the past week. For each item, the scale is rated as follows: 0=’not at all’=’not relevant’; 1=’a little’; 2=’a lot’; 3=’very much’=’yes’ in question 7, with an overall scoring system of 0 to 30; a high score is indicative of a poor QoL. The DLQI will be assessed at time points according to in Section 10.2.

- Handling missing items from DLQI
 - i. If one question is left unanswered this is scored 0 and the scores are summed and expressed as usual out of a maximum of 30.
 - ii. If two or more questions are left unanswered the questionnaire is not scored.
 - iii. If question 7 is answered 'yes' this is scored 3 even if in the same question one of the other boxes is ticked.
 - iv. If question 7 is answered 'no' or 'not relevant' but then either 'a lot' or 'a little' is ticked this is then scored 2 or 1.
 - v. If two or more response options are ticked for one question, the response option with the highest score should be recorded.

vi. The DLQI can be analyzed by calculating the score for each of its six sub-scales. When using sub-scales, if the answer to one question in a sub-scale is missing, that sub-scale should not be scored:

Symptoms and feelings	Questions 1 and 2	Score maximum 6
Daily activities	Questions 3 and 4	Score maximum 6
Leisure	Questions 5 and 6	Score maximum 6
Work and School	Question 7	Score maximum 3

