Patients will be instructed on using the patient diary to record their Sleep Quality NRS at the screening visit. Clinical sites will check and remind the patient to complete the diary according to the time points in Section [10.2](#).

The baseline Sleep Quality NRS score is defined as the prorated average of the sleep quality NRS scores reported continuously for 7 days right before the baseline visit (i.e. study day -7 to day -1). For post-baseline Sleep quality NRS score, the weekly mean of daily sleep quality score is calculated as the average of the available reported daily sleep quality score within the week. For example, if there are 3 scores available in a week, the prorated average = (score1 + score2 + score3)/3.

Patient Global Impression of Disease (PGID)

The PGID is an assessment instrument used by the patient in clinical studies to rate their eczema symptoms during the past 7 days.

Patients will rate their disease based on the 5-level scale as follows:

“Overall, how would you rate your eczema symptoms during the past 7 days?”

- No symptoms
- Mild
- Moderate
- Severe
- Very severe

The PGID score will be assessed at time points according to Section [10.2](#)

Patient Global Impression of Change (PGIC)

PGIC will be measured using a patient administered tool.

Patients will respond to the following question based on the 7-level scale as follows:

“Compared to before you started the study, how would you rate your eczema now?”

- Much better
- Moderately better
- A little better
- No change
- A little worse
- Moderately worse
- Much worse

The PGIC is an instrument used by the patient in clinical studies to compare their eczema symptoms from the beginning of the study to when they completed the assessment.

The PGIC score will be assessed at time points according to Section [10.2](#).

Colorimetry Measurement (Sub-study)

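### SAP 6.3 fixes diary weeks by study day, but Sleep Quality is collected before each visit, so an off-target visit can leave few or no scores in the analysed week

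*SAP*

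**What the plan says.** SAP 6.3 has two mapping rules. Visit-based data use wide windows that leave no gaps (week 24 is study day 156 onwards). Diary data have their own rule, introduced by "For the daily collected ePRO data, the analysis visit windows will be implemented following the procedure below", and the blocks are "2 to 8 = week 1, 9 to 15 = week 2, etc, with 7-day intervals between visit windows".

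For Sleep Quality NRS, footnote 11 to Protocol Table 1 says "Sleep Quality NRS is to be collected daily for 7 days immediately preceding the baseline visit and all subsequent visits", and the Table 1 row agrees. Protocol 9.2.2.1.2, repeated in SAP 10.3, words it differently: "then daily during the week before each planned visit". Table 1 allows 7 days either side of target at weeks 8, 12, 16, 20 and 24, and 3 days at weeks 2 and 4.

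Peak Pruritus NRS is a continuous diary: "Participants will complete the rating scale daily throughout the entire study (baseline and preceding 7 days and treatment period".

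After baseline, SAP 10.3 scores Sleep Quality so that "the weekly mean of daily sleep quality score is calculated as the average of the available reported daily sleep quality score within the week". For Peak Pruritus, "the mean weekly NRS is calculated as the prorated average of the reported daily NRS within the week". Neither sets a minimum number of daily scores. By contrast, inclusion criterion 7 requires 4 of 7 for the baseline itch average.

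**The concern.** Sleep Quality collection moves with the visit if footnote 11 is taken at face value. The analysis block does not move. No rule in SAP 6.3 or 10.3 connects the two, and the remapping of unscheduled, early-termination and end-of-study visits applies to visit dates, not diary entries.

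Change from baseline in weekly average Sleep Quality is a secondary endpoint at each visit. A participant who attends inside the permitted window and completes every diary entry can therefore have most of those entries assigned to a week that is not a scheduled visit. The analysed value then rests on fewer nights, or is missing, because of the appointment date alone. SAP 5.7.2 summarises observed data, so an empty block removes that participant from that visit's sleep summary, while EASI from the same visit is kept.

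Peak Pruritus has a narrower version of the problem: the diary has to stop somewhere, and an early last visit can stop it before the week 24 block has filled.

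**Working it through.** **Inputs.** Block rule and visit windows from SAP 6.3; target days and tolerances from Protocol Table 1; collection periods from Table 1, footnote 11, Protocol 9.2.2.1.1 and 9.2.2.1.2.

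**Reproducing the SAP blocks.** Week k = study days 7(k−1)+2 to 7k+1. For k = 1 this gives 2 to 8, and for k = 2 it gives 9 to 15, as stated. Week 8 is 51 to 57 and week 24 is 163 to 169. Each scheduled block ends on its target day T (15, 29, 57, 85, 113, 141, 169), so the block is T−6 to T.

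**Sleep Quality, collection following the actual visit.** For a visit on day D = T+d, the 7 preceding days are D−7 to D−1. Scores inside the block are the overlap of T+d−7 to T+d−1 with T−6 to T. The second row counts the visit day instead (D−6 to D), where the overlap is 7 − |d|.

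| d | −7 | −6 | −5 | −4 | −3 | −2 | −1 | 0 | 1 | 2 | 3 | 4 | 5 | 6 | 7 |
|---|---|---|---|---|---|---|---|---|---|---|---|---|---|---|---|
| D−7 to D−1 | 0 | 0 | 1 | 2 | 3 | 4 | 5 | 6 | 7 | 6 | 5 | 4 | 3 | 2 | 1 |
| D−6 to D | 0 | 1 | 2 | 3 | 4 | 5 | 6 | 7 | 6 | 5 | 4 | 3 | 2 | 1 | 0 |

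- Week 24 visit on day 162: collected days are 155 to 161. Day 155 falls in week 22 and days 156 to 161 in week 23; none is in week 24.
- Week 24 visit on day 176: collected days are 169 to 175. One falls in week 24 and six in week 25.
- Weeks 2 and 4 (d from −3 to 3): 3 to 7 scores on the first row, never zero.

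**Average, which needs an assumption.** The documents do not say how visits spread around target. Using the first row:

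- Even spread over ±7 days: 49/15 = 3.3 of 7.
- Triangular spread peaking on target, weights 8 − |d|: 273/64 = 4.3.
- Even spread within ±3 days: (3+4+5+6+7+6+5)/7 = 36/7 = 5.1.
- All visits on target: 6.

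**Sleep Quality, collection following the target date.** Collected days are T−7 to T−1 and the block is T−6 to T. The overlap is 6 of 7 whatever the visit date, provided the diary is still running.

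**Peak Pruritus at week 24.** Assume the diary stops at the last visit, which is inferred from daily collection through the treatment period. The block is days 163 to 169.

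| Last visit (day) | 162 | 163 | 164 | 165 | 166 | 167 | 168 | 169 or later |
|---|---|---|---|---|---|---|---|---|
| Visit-day entry counted | 0 | 1 | 2 | 3 | 4 | 5 | 6 | 7 |
| Not counted | 0 | 0 | 1 | 2 | 3 | 4 | 5 | 6 on day 169, then 7 |

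For participants still in the study, late visits and earlier scheduled weeks lose nothing, because the diary is daily.

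**The case against.** The strongest reply is textual. Protocol 9.2.2.1.2 and SAP 10.3 tie Sleep Quality collection to the *planned* visit. If that means the target date, the fixed blocks capture 6 of 7 scores and there is almost no problem. The phrase *within the week* in SAP 10.3 could also mean the collection week just described, not the block in SAP 6.3. This stands as a real ambiguity, but it does not remove the point: Table 1 and footnote 11 refer to the visits themselves, and SAP 6.3 covers all daily diary data without exception. The same section of SAP 10.3 sets the Sleep Quality baseline at days −7 to −1, against −6 to 1 in SAP 6.3 (6 of 7 days shared), so the two sections already differ.

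The second reply is about size, and it also stands. Loss is usually partial, Protocol 9.1.3 asks sites to keep participants on schedule, and weeks 2 and 4 are never empty. Fixed study-day weeks are a legitimate choice for a truly daily diary, because they hold treatment time constant.

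A reader might infer more than the documents support:

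- *Compliant participants are dropped.* With no minimum number of scores, one entry gives a weekly mean. The block is empty only at 6 or 7 days early (or at exactly 7 days either way if the visit day counts).
- *About half of all sleep scores are lost.* This needs an even spread over ±7 days, which nothing in the documents supports.
- *Week 24 itch is lost whenever the last visit is early.* It is wholly lost at 7 days early (6 or 7 if the visit-day entry does not count); smaller shifts shorten the week.
- *Week 24 is the main pruritus time point.* The endpoints are defined at each visit through week 24, and none is singled out.

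**Conclusion.** The mismatch holds for Sleep Quality on the reading in Table 1 and footnote 11. At weeks 8 to 24 the analysed week holds between 0 and 7 of the 7 collected scores depending on visit date, and a reported weekly average may rest on a single night. The counts for each visit date are exact for that reading. The average loss is not known: 3.3, 4.3 or 5.1 of 7 scores retained under the three spreads shown, and 6 if every visit is on target.

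For Peak Pruritus the effect is an edge case at week 24 with an early last visit, and it rests on the diary ending at that visit. In the extreme, a last visit on day 162 gives a week 24 EASI but no week 24 itch value.

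Only secondary descriptive summaries are affected. The study plans no inference, and EASI-75 at week 24 is untouched. This should be corrected, but it does not threaten the primary result.

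**What to change.** In SAP 6.3:

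- **Sleep Quality.** Average the scores from the 7 days immediately before the actual visit, and assign the result to the analysis visit to which that visit maps. All 7 collected scores are then used at every permitted offset.
- **Wording.** Align the planned-visit text in Protocol 9.2.2.1.2 and SAP 10.3 with Table 1 and footnote 11. Confirm first which date the diary is keyed to: if it is the target date, the existing blocks already capture 6 of 7 scores and the anchor only needs stating.
- **Peak Pruritus.** Keep the fixed blocks, with one exception. If the last visit maps to week 24 (study day 156 or later) and falls before day 169, use the last 7 diary days up to that visit for week 24. Do not apply this to earlier withdrawals: without the day 156 limit, a participant leaving on day 30 would have days 24 to 30 reported as week 24, which is an unplanned carry-forward.

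The cost is SAP wording and a small programming change, with no new data. The trade-off is that the averaged week no longer sits at an identical study time for every participant.
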